7.1 DATA MANGEMENT, SECURITY & ANALYSIS

7.2 Power Considerations and Sample Size Calculation (Aim2)

Sample Size and Power Calculation. The study plan is to enroll 80 participants with 1:1 random assignment to the intervention arm and the control arm (i.e., 40 in each arm). Compared to a large- scale randomized trial, we do not expect that this pilot trial will have power to detect many of the effects that would be of scientific or policy significance. This is consistent with the aims of this pilot grant mechanism, where budgetary limitations necessitate small sample sizes. Group means on continuous variables typically begin to stabilize by 20-30 participants. Thus, a sample size of 40 participants per group should provide relatively stable group means for the intervention and control conditions, even with some sample attrition.

Study Design. Participants in the intervention group will be able to access the MyPEEPS intervention from baseline until the end of month 3, and the control arm (delayed intervention) will have access to the MyPEEPS App from months 4-6.

Overview of Data Collection Time Points. We will conduct simultaneous assessments for both study arms at baseline, 3 months, and 6 months. We will also collect an immediate post-intervention assessment for the delayed intervention arm. The delayed intervention design is essentially a cross-over design in which data are collected in parallel from both study arms through the primary endpoint - 3 months post-randomization. The arms are then crossed over, which has multiple benefits, including: 1) for ethical reasons per our experience with transgender populations, the delayed intervention group receives the potential benefit of the intervention at the point of cross-over; 2) at the 6-month follow-up, it provides for a test of the durability of the intervention effect in the intervention group (i.e., 3 months post-intervention, pre-post); 3) it provides an additional secondary test of the intervention effect in the delayed intervention arm (pre-post); and 4) it provides additional time points (and power) in the intervention group, to test moderators of the trajectory of sexual risk over time.

7.3 Data and Safety Monitoring

7.3.1 Training on Human Subjects and Data Safety and Monitoring.

All proposed staff have participated in the NIH required trainings for conduct of studies that involve human subjects and any future study staff will do so upon hiring. Training for all staff

includes (but is not limited to) Protection of Human Subjects, Informed Consent, Good Clinical Practice, Quality Management, Confidentiality, and Reporting of Adverse Events, REDCap data entry and management. If any study staff discovers any untreated condition (e.g., onset of physical or mental health condition), they will refer participants to appropriate treatment immediately.

7.3.2 Data Management and Data Quality

Columbia University will be responsible for computerized survey programming, data capture, management, and analysis. All study information will be identified through the Participant Identification Number (PID) on all forms and computerized files. Data files will be exported from the ACASI program and imported into the SPSS database for storage. Computer data files never have any identifying information and are encrypted prior to transfer between study sites. Data entered into the SPSS database will not include any identifying information. Only authorized users with a login name and password will be able to open the computerized survey, and only those with administrative privileges will be able to access data. The study research assistant (RA) will use a login name and password to gain access to the software to administer it to a participant, but they will have no ability to access the saved data. The database, data structure, and data quality will be routinely reviewed by [name], and the Data Manager will set up the database, check data quality, and prepare the data for use. The Multiple PIs will work closely to plan analyses for various purposes, including for hypothesis testing and manuscript development and reports. Data quality will be examined before statistical analyses are conducted, including examination of missing data,

assessment of distributional assumptions, and identification of outliers. In addition to data quality, the comparability between intervention and control groups will be carefully examined, including baseline balance and differential attritions at all waves of follow-up. While differences are not expected from the randomized design, it is prudent to plan for this contingency so that sufficient follow-up data and appropriate statistical methods can be used for intent-to-treat analyses. The psychometric properties of instruments will also be examined, as will the patterns of missing data.

7.3.3 Data Monitoring

For the study, weekly reports for the sites will be created by the data manager to review relevant app engagement data, barriers with recruitment/enrollment and retention, urine sample collection, compliance with the protocol, and accuracy and completeness of the records. The investigative team will hold reoccurring conference calls, and these reports will be briefly reviewed by the team at these meetings. These regular reviews will ensure close communication between the research assistants, quickly identify missing data points, and ensure consistent management of any issues with the protocol between sites.

Data quality will be examined before statistical analyses are conducted, including examination of missing data, assessment of distributional assumptions, and identification of outliers. In addition to data quality, the comparability between intervention and control groups will be carefully examined, including baseline balance and differential attritions at all waves of follow-up. While differences are not expected from the randomized design, it is prudent to plan for this

contingency so that sufficient follow-up data and appropriate statistical methods can be used for intent-to-treat analyses.

7.3.4 Data Safety and Monitoring Board

The contact Principal Investigator (PI) will enlist a Data and Safety Monitoring Board (DSMB) to oversee the data, safety elements, and overall integrity of the study. The DSMB will: 1) monitor recruitment, enrollment, and adherence of study participants; 2) formulate criteria for modifying or discontinuing the intervention of individual subjects; and 3) review serious adverse events (SAEs). The objectives of the DSMB will be to assess the safety of the intervention trial and to assure the highest degree of subject safety. We will work with the NIMH to identify individuals to serve in this role. Monitoring board membership will be reviewed and approved by NIMH. Should there be any questions regarding the independence of the monitoring board it will be addressed and corrected if necessary.

The biostatistician with clinical trials expertise and the data manager will prepare monitoring reports in advance of every DSMB meeting. The DSMB will remain blinded to randomization status unless, for safety reasons, the DSMB, in consultation with the NIMH Program Administrator, decides it is important to unmask the data.

The DSMB will: 1) review the protocol as funded and make suggestions for any changes (especially safety related); 2) assess the endpoints suggested by the investigators; 3) review study progress by reviewing recruitment, retention, and compliance of participants and data quality; 4) determine formatting for data reports; 5) review endpoints for safety; 6) submit written reports and

suggestions to the team; and 7) add to or modify this list of objectives. The Project Director will document the minutes of the meetings and distribute to the Chair of the DSMB for final approval or revision.

7.4 Adverse events

7.4.1 Adverse event assessment

We anticipate that the Data Safety and Monitoring Board will define study-specific serious adverse events (SAEs). While we do not anticipate any SAEs, we will suggest looking for imbalance among treatment arms with regard to the following criteria: safety and data security and study drop-out

7.4.2 Adverse event reporting

We will follow the guidelines that require investigators to promptly notify the IRB (within days of the occurrence) when SAEs occur. SAEs will be defined as death, life threatening illness, hospitalization or prolongation of hospitalization, and persistent/significant disability. The IRB requires that any SAE that is unexpected and related or possibly related to the research intervention must be reported. SAEs that are unrelated to the research intervention do not have to be reported to the IRB (however, we will report these to the monitoring entity and NIH). Risks that are described in the protocol and consent form do not have to be reported as SAEs unless

the expected SAE occurs more frequently or is more serious than expected. One exception to this rule is in the case of a death. All deaths must be reported, whether or not the death was related to the research.

7.5 Data Security and Privacy

Beginning with the development process and throughout the research project, we will follow the privacy and security principles set forth at healthhit.gov. Our team is familiar with the importance of the privacy and security of personal health information to engender individual trust in the use of health IT applications. We have expertise and experience in this domain as we have developed a number of health IT systems funded through NIH and the Agency for Healthcare Research and Quality for persons living with HIV whose personal health information is usually held to higher security standards than traditional patients, as HIV has historically been a stigmatized disease.

We built the MyPEEPS App (NIMHD U01 MD011279) which is housed on the CUIMC IT servers. The CUIMC servers are located in a secure datacenter, with necessary redundancies. Currently the network can be accessed remotely via Virtual Private Network with a Citrix solution being developed. All servers have HIPAA compliant security.

CUIMC has an Information Security Office (ISO) that facilitates all aspects of information security risk management at CUIMC, with a particular focus on threat management and HIPAA compliance. This includes administration and enforcement of information security policies on campus. ISO also provides guidance to CUIMC schools and departments regarding any information security concerns they may have. The ISO collaborates with the entire CUIMC community to protect the confidentiality, integrity, and availability of critical information and computer resources. The ISO strives to implement secure computing infrastructure and practices with sensitivity to CUIMC's educational and research environment. Columbia University has an information security charter which is the foundation of all of the work carried out by [name] and her research team. In specific, [name] will work with the CUIMC IT server group and the information security office to protect the confidentiality, integrity, and availability of participants' data. Confidentiality means that information is only accessible to authorized users. Integrity means safeguarding the accuracy and completeness of data and processing methods. Availability means ensuring that authorized users, such as research participants, have access to data and associated information resources when required.

Prior to assent and consent, study participants will be informed as to what data the applications will collect. Data will be encrypted and stored securely on the CUIMC IT servers. As a starting point for ensuring privacy and security, all smartphones will be password-protected. In addition, there will be an additional password for the App so that only study subjects will be able to open the App.

7.5.1 Procedures to Ensure Compliance with Monitoring Plan and Reporting Requirements

Biweekly reports for the sites will be created by the study statistician to review relevant app engagement data, barriers with recruitment/enrollment and retention, laboratory and medical records, compliance with the protocol, and accuracy and completeness of the records. The

investigative team will schedule biweekly conference calls, and these reports will be briefly reviewed by the team. These regular reviews will ensure close communication between the research assistants, quickly identify missing data points, and ensure consistent management of any issues with the protocol between sites.

7.6 Data Analysis Plan for Aim 2

Assessment of feasibility and acceptability of the intervention (Table 5). We have specified the following measures of feasibility and acceptability: Retention Rates, Compliance Rates, Dose, Eligibility Criteria, Recruitment and Enrollment, Missing Data, Study Measures(68-70).

Table 5. Measures of Feasibility and Acceptability of MyPEEPS Mobile for YTM

Constructs	Measures	Threshold (if applicable)
Retention Rates	-How many enrollees remain in the study? -Are they about the same in both arms?	At least 80% will remain in the study.
Compliance Rates	What is the completion rate of app sessions by participants?	At least 80% will have completed at least 75% of the intervention content.
Dose	Is the dose of the intervention e.g., number of sessions adequate (assessment of paradata).	Does the dose need to be adjusted?
Eligibility Criteria	Are eligibility criteria acceptable, or do they need modification because they are too stringent?	Eligibility rates (number of individuals eligible among those approached)
Recruitment and Enrollment	What is the pace of recruitment? Barriers to recruitment and enrollment	
 Rates of refusal (number of refusals vs. enrolled among those approached) Rates of no shows
Missing Data Measures	What is the extent and patterns of missing data? Length of time and burden to the respondents	The survey questions (Number and Type) may need to be adjusted

Study Outcomes. The pilot study will be used to assess the preliminary efficacy of MyPEEPS Mobile for YTM. Our primary outcome will be the number of condomless receptive anal and/or vaginal sex acts with either a cisgender male or transgender woman. To estimate the effect size for a larger clinical trial, we will focus on the primary outcome of: Condomless receptive anal or vaginal sex acts. The measures listed in Table 6 have been used in our MyPEEPS trial and piloted with 49 YTM as part of our formative work for this application. We will collect all measures at baseline, 3 and 6 months, other than demographic variables which will only be collected at baseline. We also ask participants to report on their own knowledge of their most recent partners' use of PrEP or ART medications. Given the unreliability of perceptions of partner-related risk in particular(71), we will use these data for a secondary sensitivity analysis (see below). This study is not powered for efficacy or tests of moderation or mediation; nonetheless, the purpose of the inclusion of these factors is to measure the impact of the intervention on

them as intermediate targets given their potential role in behavior change.

Table 6. Outcome Measures

Demographics

Sociodemographic (e.g., age, race/ethnicity level of education, housing status)

Newest Vital Sign(72)

Short Test of Functional Health Literacy (S-TOFHLA)(73)

Transgender Congruence Scale(74)

Measures of Hormone Use

Primary Outcome Measures

Condomless receptive anal and/or vaginal sex (adapted from AIDS-Risk Behavior Assessment)(68-70)

Intermediate Outcome Measures

Self-efficacy for safer sex and situational temptation for unsafe sex(75)

Condom Errors(76)

Health Protective Communication Scale(77)

HIV-Knowledge Questionnaire – HIV-KQ-18(78)

Alcohol and Substance Use(79)

Sexual Behavior Index(80)

Secondary Outcomes

nPEP and PrEP Use

Self-reported HIV and STI Testing

Partner(s) PrEP Use, PrEP Adherence or Viral Suppression (if partner is HIV+)

Program Evaluation

Knowledge of and beliefs about the content of the MyPEEPS Mobile intervention

MyPEEPS intervention acceptability and tolerability(81)

Paradata

Data Analysis. All multivariate analyses will be preceded by standard descriptive bivariate analyses to describe key variables and relationships among key variables. These analyses will include means, frequency tables, histograms, and examination of distributions. All statistical tests will be two-sided tests with the level of significance at 0.05(60).

Outcomes: This study will examine whether the intervention will reduce the number of condomless receptive anal or vaginal penile sex with either a cisgender male or transgender woman; the primary outcome is a count measure (Table 6 - Outcome Measures). We assume that all count outcome variables follow Poisson or negative binomial (NB) distribution, $y \sim \text{Poi}(\lambda)$ or $y \sim \text{NB}(\lambda, \kappa)$ and all percentage outcomes follow binomial distribution, $y \sim \text{bin}(n, p)$. Let the expected value of outcome, $E(y) = \varphi$, so $\varphi = \lambda$ for count outcomes and $\varphi = p$ for binary outcomes. We propose the following generalized linear mixed model (GLMM) to analyze all outcomes. The level of analysis

will be assessed at each data point. For person i and data assess wave W (i.e. baseline, 3, and 6 months):

$$+ \mu_i,$$

where $h(\cdot)$ is the link function for the GLMM. We will use log-links (Poisson or NB regression) for count

Table 7. Codes for design variables

Months	Intervention			Delayed Intervention		
	Arm	W	INT	Arm	W	INT
Baseline	0	0	0	1	0	0
3 mos	0	1	1	1	1	0
6 mos	0	2	1	1	2	1

outcomes and logit-links (logistic regression) for binary outcomes. μ_i iid~ $N(0, \sigma^2)$ are personal level random effects for the intercept. Variables Arm, W, and INT are design variables. The codes for the design variables are presented in Table 7. Variable Arm is the indicator for intervention arms (0=intervention arm and 1=delayed intervention arm); variable W is data assess wave indicator (0=baseline, 1=3 months, 2=6 months); and variable INT is the intervention indicator (0=pre-intervention, and 1=post-intervention). COV is a vector of personal level covariates at the baseline, such as age, sex, etc., and $\mathbf{XXXXXXXXXXXXXX}$ is a vector of time-dependent covariates assessed at each wave of data for each subject controlling for potential bias between two arms. This model will include both baseline personal level covariates as well as personal-wave level covariates to control for different types of potential confounders. Regression parameter β_3 is the mean value change for the outcome variables between pre- and post-intervention and measures the impact of the intervention on each outcome variable. For the Poisson or NB models, $\exp(\beta_3)$ is the ratio of mean counts (i.e., risk ratio) between post and pre-intervention. For the logistic models, $\exp(\beta_3)$ is the odds ratio between pre- and post-intervention. If the count outcome has excess 0s (for example, much greater than expected number of people who had 0 receptive condomless anal or vaginal sex act as comparison to number of people who had 1,2,..,etc. number of receptive condomless anal or vaginal sex acts), the above Poisson or negative binomial GLMMs can be extended to zero-inflated Poisson or negative binomial models(82).

Sensitivity Analysis: To address whether PrEP use by the partner or the viral suppression status of a HIV+ partner affects the outcome, we will ask participants if their partner(s) use PrEP, use PrEP regularly or if their partner is HIV+ are virally suppressed and we will conduct a counterfactual sensitivity analysis(83, 84), which includes the following steps: 1) We will examine if there is any difference in partners' PrEP use and/or HIV status between pre- and post- intervention. This comparison can be done using the same GLMM for the primary outcome, treating partners' PrEP use and/or HIV status as the outcome. 2) We will examine the impact (or association) of partners' PrEP use and/or HIV status on condomless anal sex based on a GLMM or LMM. 3) If there are difference in step 1) AND significant effects in step 2), our estimation of the impact of intervention on main outcome will be biased. We will correct estimates by estimating the true causal effect of impact on main outcome.

Secondary Outcomes: We will use GLMM to analyze secondary outcomes with appropriate choice of link functions according to the outcomes. All analyses will be done on the final data set (baseline n=80). As an objective of this R34, we will quantify intervention effect sizes of program impact on risky sexual behavior and substance use. To gauge effect sizes, we will use Cohen's d (85) and Hedge's g corrected for sample size(86), both of which express the average amount of individual change between experimental and control groups in terms of units of standard deviation. In addition, we will also estimate the correlations within outcomes across timepoints as the magnitude of this correlation can have significant impact on power to detect effects in repeated measures analyses. These estimates of effect size will enable us to accurately determine the sample size necessary to achieve adequate statistical power in future investigations of program efficacy within this population. We will use the following outcomes to estimate the statistical power for a larger study: (1) number of receptive condomless anal or vaginal sex acts with male partners (e.g., cisgender males and transgender women) during the past 3 months, and (2) number of HIV tests during the past 3 months. We will estimate the statistical power to examine overall effect with the total subjects to conduct stratified analysis to examine the effects in some subgroups (such as by sex and/or for some racial/ethnicity

subgroups). All power estimations will be based on $\alpha=0.05$ and 2-sided tests. We will base our power estimates on the retention rate at the 3-month and 6-month follow up assessment for each study arm, the intra-cluster correlation.

Given these parameters, if the findings from the pilot study indicate that at post-intervention the number of receptive condomless anal or vaginal sex acts during the past 3 months decreased by 45% or a relative risk (RR) of 0.55, then for a future R01 study, we will have at least 99% power to detect such difference for a total sample size of 320. Secondly, for the stratified analyses, we will have 87% power to detect a relative risk of 0.55 in subgroups with a sample size of 64. For the HIV testing outcome, if the number of HIV tests during the past 3 months increases by 75% (i.e., RR

=1.75), a sample size of 320 participants will have an 84% power to detect such difference.

Paradata: we will assess participants' use of the App over time through the collection of paradata(87), specifically the page accessed, time stamp and device type. Paradata is considered "free" in that it does not require any additional effort from the user(88) **Data Analysis:** At the individual level, we will understand participants' use of the App over time through the collection of paradata(87) which is "free" in that it does not require any additional effort from the user(88). To explore barriers and facilitators to widespread implementation of MyPEEPS Mobile for YTM, we will collect data during intervention, implementation, and after the trial has ended. The primary paradata to be collected are page accessed, time stamp, and device type. From these data, we will derive the following use of data for each session: duration on each page, page progression through the application, time from login to result, and total time from login to logout. We will analyze the data at the individual-level (i.e., user-level), application-level, page-level, and session- level and assess how these differ by demographic characteristics, technology use, and outcome measures. Additionally, we will measure the amount in bytes of user data transmitted. Importantly, longitudinal analysis will determine if the user experience changes with repeated use. The paradata collected from each page will be analyzed to generate a "heatmap" of user-interaction (i.e., the distribution of activity for each link/button) that will inform user duration on each page of the App and user interaction with App content, contact pages, and the help page. We will explore usability issues with consideration for how many times users accessed help and what page of the App referred them to the help, implying the need for clarification. We will analyze differences in

aggregated data by demographic group (e.g., age) to better understand engagement with the intervention and potential facilitators and barriers to App use.

7.6.1 Data Analysis for Aim 3

All in-depth interviews will be transcribed verbatim and then coded. The development and application of a coding scheme is an integral component of the data analysis process. It enables the systematic examination and interpretation of the data related to the primary analytic foci. The coding scheme is conceptualized as a multilevel structure. At the highest level are the primary analytic foci coded as headings. Specific aspects or dimensions of the headings are assigned core codes. Specific aspects or dimensions of the core codes are assigned sub-codes. We will use NVivo™ (QSR International, Victoria, Australia), a software program for qualitative analysis, to facilitate the analysis.

The following 7 steps will be used to develop the coding scheme: Step 1: Identify the principal issues discussed by participants; Step 2: Construct definitions of the primary analytic themes;

Step 3: Develop and apply core codes and sub-codes to the initial set of interviews; Step 4: Develop a provisional coding scheme; Step 5: Test and refine the provisional coding scheme; Step 6: Reconcile coding differences and construct an updated and final coding scheme; Step 7: Apply the coding scheme to the full data set and assess inter-coder reliability. After all transcripts have been coded, we will extract and examine the content of text segments linked to core codes and sub-codes relevant to understanding barriers and facilitators to the use of the MyPEEPS App. Based on the coded data, we will propose ways in which certain themes are analytically related. A careful examination of the coded text will reveal the associations among these themes and may lead to more refined data searches. Once we establish patterns of relationships among themes and issues, we will identify participants' accounts that support or refute these patterns. Identifying and accounting for cases that deviate from an interpretative pattern enables us to test and confirm the pattern's validity and robustness.

Triangulation of Findings. We will examine changes in HIV risk behaviors and its relationship to factors including but not limited to changes in substance use, alcohol use, stigma, victimization. We will triangulate the findings from our quantitative outcome measures (Aim 2) with the findings from our qualitative data (Aim 3) to better understand participants' decisions for their HIV risk behaviors.

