Randomization to Intervention and Control (Delayed Intervention) Arms. Using the randomization module in REDCap and the approach described below, there will be random or minimally biased assignment of subjects to study arms. We will use block randomization with randomly permuted blocks(56) to reduce opportunities for selection bias. The advantage of the permuted block design is that treatment assignment is pre-determined before the trial begins and then assignment remains static throughout the course of the trial(57). Blinding and random assignment will be maintained through continuous supervision by key members of the research team. All staff and participants will be kept blinded to outcome measurements during data collection(58). This technique will maintain complete randomness of the assignment of a subject to a group. Participants will be randomized based on the use of a password protected computer- generated random numbers at baseline to avoid the possibility of study staff subverting randomization as has been noted in previous studies(59). Following completion of the informed assent/consent and baseline assessment, participants will be randomly assigned to one of the two trial arms using the randomization module in REDCap(57). This will minimize the biased assignment of study subjects(60).

Intervention Delivery. If the study participant is randomized to the intervention arm, they will have access to the MyPEEPS Mobile App for the next three months. Participants randomized to the control (delayed intervention) arm will be given access to MyPEEPS Mobile at the 3-month study visit. Through our dashboard, we can monitor when participants login to MyPEEPS Mobile, time spent on each activity, and whether they are actively using the intervention or just logged in. Participants will have 3 months to complete the 4 MyPEEPS Mobile modules, which includes 25 embedded mobile activities (See [Table 3](#)).

Participants in the intervention group will be able to access the MyPEEPS intervention from baseline until the end of month 3 and the control arm (delayed intervention) will have access to the MyPEEPS App from months 4-6 (see [Figure 2](#)). **Overview of data collection time points.** We will conduct simultaneous assessments for both study arms at baseline, 3 months, and 6 months.

Intervention Arm	Baseline		Follow-Up		Follow-Up
	A	XXX	A	XXX	
Delayed Intervention Arm (Control)	A		A	XXX	A
TIMELINE	0 months		3 months		6 months

A =Assessment X =Intervention

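### A free Arm term in the primary GLMM leaves the equal-baseline constraint from randomisation unused, which modestly widens the interval for the intervention effect

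*Combined protocol and SAP*

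**What the plan says.** Section 7.6 (Data Analysis Plan for Aim 2) fits a GLMM with a log link for the primary count. Every assessment is an outcome row: "For person i and data assess wave W (i.e. baseline, 3, and 6 months"). A person-level random intercept links the three rows.

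On the fixed effects, the section states "Variables Arm, W, and INT are design variables", and "Variable Arm is the indicator for intervention arms (0=intervention arm and 1=delayed intervention arm"). Table 7 codes INT as 0, 1, 1 in the intervention arm and 0, 0, 1 in the delayed arm. The coefficient of interest, beta3, is described as the pre-to-post intervention change, which is the INT term.

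On covariates: "COV is a vector of personal level covariates at the baseline, such as age, sex, etc". The baseline count is not among those named, and as an outcome row it would not be expected there.

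On timing, section 4.5 (Randomization) says: "Following completion of the informed assent/consent and baseline assessment, participants will be randomly assigned to one of the two trial arms". Sections 4.5 and 7.2 describe the 3-month assessment as the primary endpoint and the 6-month assessment as a test of durability. Section 7.2 plans to "enroll 80 participants with 1:1 random assignment".

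The body of the model equation was not legible in the copy reviewed. That Arm enters as a free main effect is inferred from the list of design variables and from beta3 being the INT coefficient. No text sets the baseline means of the arms equal.

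**The concern.** At baseline the coding of W and INT is identical in the two arms, so the only term that can separate their means is Arm. The baseline assessment is complete before allocation, so in expectation that separation is zero. The model therefore spends data estimating a quantity that the design already fixes.

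The cost is precision. A main product of this 80-person pilot is an effect estimate to plan a larger trial, so an avoidable widening of its interval is worth removing if removal is free. The named baseline covariates do not recover the loss. Sex assigned at birth is fixed by the eligibility criteria, and age does not stand in for the baseline count.

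**Working it through.** **The plan's own figures.** The documents give no standard error, interval width or power for the pilot. The only related figures are for a future trial at a rate ratio of 0.55: 87% power at N=64 and at least 99% at N=320. They agree with each other. |ln 0.55| = 0.598, and 87% power at two-sided 0.05 implies SE = 0.598/(1.960 + 1.126) = 0.194. Scaled by sqrt(64/320), this is 0.0866, which gives power above 99.99% at N=320. Neither figure bears on the Arm term.

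**Inputs.** From the documents: 40 per arm, three waves, INT coding from Table 7, random intercept only (exchangeable correlation on the link scale). Assumed: rho, because the plan intends to estimate it from the pilot; complete data; equal variance at each wave.

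**Step 1: what the planned model estimates.** Let d0, d3 and d6 be the arm differences at baseline, 3 and 6 months, each with variance 2σ²/n and pairwise correlation rho. INT differs between arms only at 3 months.

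- Arm kept: beta3 = d3 − ½(d0 + d6).
- Arm dropped, single INT kept: beta3 = d3 − [rho/(1+rho)](d0 + d6).

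**Step 2: variances, in units of 2σ²/n.**

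- Arm kept: 1 + ¼(2 + 2rho) − 2rho = 1.5(1 − rho).
- Arm dropped: 1 − 2rho²/(1+rho) = (1 − rho)(1 + 2rho)/(1 + rho).
- Ratio dropped/kept: (1 + 2rho)/[1.5(1 + rho)].

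**Step 3: numbers** (n = 40, σ = 1).

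| rho | SE, Arm kept | SE, Arm dropped | Variance ratio dropped/kept | SE increase from keeping Arm |
|---|---|---|---|---|
| 0.2 | 0.245 | 0.216 | 0.78 | 13% |
| 0.3 | 0.229 | 0.207 | 0.82 | 10% |
| 0.5 | 0.194 | 0.183 | 0.89 | 6% |
| 0.7 | 0.150 | 0.145 | 0.94 | 3% |

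The increase is at most 22%, at rho 0, and vanishes as rho approaches 1. Treating W as categories or as linear gives the same ratio in balanced data. With 20% missing at each follow-up the increases at rho 0.3, 0.5 and 0.7 are still 10%, 6% and 3%.

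**Step 4: check on the count scale.** Negative binomial random-intercept models were simulated with 40 per arm and a rate ratio of 0.55. Assumed settings were mean count 4, random-intercept SD 0.6 to 1.3 and shape 1 to 3, with 60 runs for each of four settings. The median ratio of model SEs, kept to dropped, was 1.05 to 1.14. The empirical SDs were smaller without Arm in three settings and about equal in the fourth (0.269 kept, 0.272 dropped), which 60 runs cannot resolve. Mean error on the log scale lay between −0.046 and −0.002 for both models, so neither showed material bias.

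**Step 5: separate 3- and 6-month treatment terms.** With the baseline means equal and both follow-up contrasts free, the variance of the 3-month effect is 1 − rho². Its SE relative to the planned model is sqrt[(1 + rho)/1.5]: 0.93 at rho 0.3, 1.00 at 0.5 and 1.06 at 0.7.

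**The case against.** A free arm term in a longitudinal GLMM is conventional and valid, and the section says "This study is not powered for efficacy or tests of moderation or mediation". No interval-width target is set. Effect sizes will also be expressed as Cohen's d and Hedges' g, and the illustration of future power starts from a point rate ratio. On this view a few per cent of interval width changes little. That is right about scale, and it limits the point to an efficiency improvement.

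Three stronger readings are tempting, and the documents do not support them.

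- *That the baseline count is thrown away.* It is an outcome row with weight −½ in the planned estimate. At rho above about 1/3 the planned model is more precise than an unadjusted 3-month comparison.
- *That the loss is a quarter to a third of the variance.* The ratio (1 + rho)/2, which gives 0.65 at rho 0.3 and 0.75 at 0.5, compares models with two waves or wave-specific treatment terms. The plan has three waves and one INT term.
- *That the effect is a plain difference in change from baseline.* Under Table 7 the 6-month difference enters with the same weight as the baseline difference.

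It can also be objected that dropping Arm forces the arms to be equal at 6 months, although durability is an open question. The planned model already forces the 6-month difference to equal the baseline difference, because INT is 1 in both arms by then. Dropping Arm adds only the baseline constraint, which holds by design. If the arms do differ at 6 months, the planned estimate absorbs half of that difference. The reduced model absorbs rho/(1 + rho), which is 0.23 at rho 0.3 and 0.33 at 0.5.

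**Conclusion.** The point holds as a modest efficiency loss. Keeping Arm widens the SE of beta3 by about 3% to 13% for assumed rho between 0.7 and 0.2. At rho 0.3 the loss is equivalent to needing about 22% more participants (1/0.82), and at 0.5 about 12% (1/0.89).

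The direction is secure for any rho below 1 under the stated assumptions. The size rests on a correlation that the documents do not give, on exchangeability, and on the inference that Arm is a free main effect. If the full equation has no Arm main effect, the point falls away.

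A reader might infer that the planned analysis is biased or that its tests at the 0.05 level are invalid because of this term. Nothing in the documents or the calculations shows that.

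**What to change.** In section 7.6, remove the Arm main effect from the primary GLMM. Keep baseline, 3 and 6 months as responses, W as wave categories, the single INT term and the person random intercept, and state that both arms share one baseline mean because allocation follows the baseline assessment. Keep the baseline rows of all 80 randomised participants in the model, since the constraint applies to the randomised groups. Chance baseline imbalance is still adjusted for, through the within-person correlation.

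If separate 3- and 6-month treatment terms are wanted to examine durability, present that constrained-baseline model as an additional analysis. Note that its 3-month interval is narrower than the planned model's only when rho is below about 0.5, and that it answers a different question from the single INT term.

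The cost is one line of model specification for the primary analysis, with no extra data or visits.
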